5.6 Requirements at the beginning of each cycle

A new course of treatment may begin on the scheduled Day 1 of a new cycle if:

- The ANC is $\geq 1,000/\mu\text{L}$;
- The platelet count is $\geq 50,000/\mu\text{L}$;
- Any lenalidomide-related allergic reaction/hypersensitivity or sinus bradycardia/ other cardiac arrhythmia adverse event that may have occurred has resolved to \leq grade 1 severity;
- Any other lenalidomide-related adverse event that may have occurred has resolved to \leq grade 2 severity.

If these conditions are not met by Day 1 of a new cycle, the subject will be evaluated weekly and a new cycle of therapy will not be initiated until the toxicity has resolved as described above. Patients unable to initiate a new cycle of therapy within 4 weeks due to treatment related toxicity will be removed from study.

- If lenalidomide dosing was held during the previous cycle and was restarted with a one-level dose reduction without requiring an interruption for the remainder of the cycle, then that reduced dose level will be initiated on Day 1 of the new cycle.
- If lenalidomide dosing was omitted for the remainder of the previous cycle or if the new cycle is delayed due to lenalidomide related toxicity newly encountered on the scheduled Day 1, then the new cycle will be started with a one-level dose reduction of lenalidomide.

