5.7 Patient Withdrawal

A patient should be removed from the study whenever it is necessary to safeguard his/her welfare. Occurrence of a significant adverse event or laboratory abnormalities unexpected for these patients may also necessitate discontinuation from the study. Additional reasons for removing a patient from the study are:

- Patients who participate in another investigational drug trial
- Patients' non-compliance with the protocol that can negatively affect the treatment effect
- Patients who express a desire to withdraw from the study (the patient has the right to withdraw for any reason without prejudice)
- Evidence of progressive disease would require withdrawal of the patient from the study.
- Any other reasons deemed by the principal investigator and treating physician.
- Patients who must discontinue use of either CT-011 or lenalidomide

The reason for any patient withdrawal from the study should be recorded on the case report form (CRF) and the occurrence should be reported to the principal investigator by email. These patients who withdraw from the study in the phase II portion of the trial will not be replaced. When a patient is removed from the study, he/she will receive treatment according to the standard of care (SOC) in the medical center and will be followed-up according to the study schedule whenever possible.

A patient who is removed from the study by the investigator due to an adverse event (AE) or serious adverse event (SAE) will be followed until resolution of the toxicity to Grade 1 or baseline. All the tests that are required to assess the patient condition will be made as frequent as necessary until the AE or SAE has been resolved. Samples that have already been obtained will be processed.

A patient who withdraws consent before starting the study will not be followed up.

A patient who is removed from the study by the investigator since he/she did not keep the appointments will be hard to follow given the circumstances. The extreme situation of this occurrence is a patient who is defined as "lost to follow-up". Attempts to follow up on the subject will be made as long as the consent has not been withdrawn by the subject. Samples that have already been obtained will be processed.

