6.3 Clinical outcome definitions

Time to progression: TTP will be defined as the time from start of treatment until the date he or she has progression or dies. Any subject who has received study treatment but has neither progressed nor died will be censored on the date of his or her last tumor assessment. A subject who has not received study treatment and who has neither progressed nor died will be censored on the day he or she was enrolled.

Progression Free Survival: PFS will be defined as the time from study entry until disease progression or death at trial closure for the per protocol population. Patients who withdraw from the trial prior to disease progression and who are either lost to follow-up, die or who begin alternative treatments prior to progression, will have their data censored as of the date considered to be lost to follow-up, date of death, or the first day of alternative therapy.

Time to Response: A subject's time to response is defined as the time from first dose of study therapy until measurement criteria are first met for [VG]PR or CR or SD (whichever status is recorded first). Time to response is computed only for subjects whose best response is [VG]PR or CR.

Duration of Overall Response: The duration of overall response will be computed for subjects whose best response is either [VG]PR or CR or SD. It will be measured from the time measurement criteria are first met for complete response or partial response (whichever status is recorded first) until the first date of progressive disease or death. Subjects who neither progress nor die will be censored on the date of their last tumor assessment.

Overall Survival: A subject's survival time will be defined as the time from start of treatment to the date of his or her death. If the subject has not died, survival will be censored on last date the subject was known to be alive.

Response Rate: The tumor response rate will be defined as the total number of subjects whose best response is PR or VGPR or CR or SD, divided by the number of per protocol patients.

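### PFS censors deaths that follow withdrawal without progression, while the endpoint labelled TTP counts them; limited impact, but wrong as written (with a secondary point on conflicting survival follow-up)

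*Combined protocol and SAP*

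**What the plan says.** **PFS (6.3).** The first sentence reads "PFS will be defined as the time from study entry until disease progression or death at trial closure for the per protocol population". The second sets an exception for "Patients who withdraw from the trial prior to disease progression and who are either lost to follow-up, die or who begin alternative treatments" before progression. Their data are "censored as of the date considered to be lost to follow-up, date of death, or the first day of alternative therapy". The documents do not define the per protocol population.

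**Other definitions in 6.3.** "TTP will be defined as the time from start of treatment until the date he or she has progression or dies"; only patients with neither event are censored. Duration of response runs "until the first date of progressive disease or death". Neither has an exception for withdrawn patients.

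**Routes to withdrawal.** 5.6: "Patients unable to initiate a new cycle of therapy within 4 weeks due to treatment related toxicity will be removed from study". 5.7: "Occurrence of a significant adverse event or laboratory abnormalities unexpected for these patients may also necessitate discontinuation from the study".

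**Status of the endpoints.** Section 2.1 lists PFS as secondary. Section 2.4 and the synopsis list TTP and OS, not PFS. Section 6.1.2 calls the PFS and OS analyses exploratory, but names PFS among the factors to be weighed if 10 or 11 of 29 patients respond.

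**Follow-up for survival.**
- 5.8.3 follows each patient for 6 months after treatment, but it and footnote p of 5.8.6 end data submission at progression or death.
- 4.4 exempts patients who stopped for progression from the monthly evaluations. It completes the study 30 days after the last subject stops medication.
- 5.7 plans monthly survival calls only for patients removed for starting a treatment the protocol does not allow. Other removed patients "will be followed-up according to the study schedule whenever possible".

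**The concern.** The same outcome, death without progression, is a PFS event if the patient was still on study and a censoring if the patient had withdrawn. Kaplan-Meier treats a censored patient as having the same later risk as those still followed, which cannot hold for someone who has died. Because removal can be caused by toxicity, deaths after a toxicity withdrawal are among those taken out of the event count.

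The labels are also partly swapped. The endpoint called TTP counts every death without prior progression and is in effect the usual PFS; the endpoint called PFS omits some of those deaths. A responder's death can end the response and still be censored for PFS. If the trial lands in the inconclusive zone, the endpoint that 6.1.2 names as an input is the more favourable of the two.

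Separately, OS is a secondary endpoint, yet the follow-up sections do not agree on whether survival status is collected once a patient has progressed.

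**Working it through.** **1. The plan's own design figures (6.1.2).** Exact binomial, n = 29, not promising at 9 or fewer responses, promising at 12 or more:
- P(X ≥ 12 | 0.25) = 0.039 (stated 4%)
- P(X ≤ 9 | 0.50) = 0.031 (stated 3%)
- P(X ≤ 9 | 0.25) = 0.834 (stated 0.83)
- P(X ≥ 12 | 0.50) = 0.868 (stated 0.87)

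All agree to rounding. The remainder is the chance that PFS becomes an input:
- ORR 25%: P(10) + P(11) = 0.081 + 0.047 = 0.127
- ORR 50%: 0.037 + 0.064 = 0.102

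**2. One death under each definition.** Take a patient removed for toxicity without progression, who starts no other therapy and then dies.

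| Definition in 6.3 | Treatment of the death |
|---|---|
| PFS, first sentence | event |
| PFS, second sentence | censored at date of death |
| TTP | event |
| Duration of response (if a responder) | end of response |
| OS | event |

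Only the second PFS sentence censors it.

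**3. Direction.** At a death time with n at risk and d events, the Kaplan-Meier factor is (n − d)/n. Recoding one event as censored gives (n − d + 1)/n. The patient leaves the risk set at the same time either way, so later risk sets do not change. The curve is equal or higher from that time on.

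**4. Size.** The documents give no number of affected deaths, so a range is assumed. Input: median PFS of 7.7 months (1.3.1, once-daily lenalidomide). With constant hazard and a share s of events recoded, the reported median is 7.7/(1 − s):
- s = 1/20: 7.7/0.95 = 8.1 months
- s = 2/20: 7.7/0.90 = 8.6 months
- s = 4/20: 7.7/0.80 = 9.6 months

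A simulation of 29 patients (exponential times, administrative censoring assumed uniform over 6 to 24 months, about 20.7 events on average) gives 8.1, 8.5 and 9.5 months. With no affected deaths the shift is nil.

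**5. OS, worst case only.** Assume that treatment ends at progression, hazards are constant, nobody dies before progression, and there is no contact later than 6 months after progression. Let λ = ln 2 / (median PFS or TTP). Solve the post-progression death rate μ so that the median OS m satisfies

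exp(−λm) + [λ/(λ − μ)] × [exp(−μm) − exp(−λm)] = 0.5.

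The share of deaths more than 6 months after progression is exp(−6μ).

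| Background medians, months | μ per month | Deaths later than 6 months after progression | OS read at the true median, no later contact | Same, half of progressed patients fully followed |
|---|---|---|---|---|
| PFS 7.7, OS 28 (1.3.1) | 0.0431 | 77% | 66% | 54% |
| PFS 3.9, OS 27 (1.3.1) | 0.0332 | 82% | 60% | 51% |
| TTP 11.1, OS 29.6 (Table 1-1) | 0.0517 | 73% | 68% | 56% |

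The correct reading at the true median is 50%. The last two columns accumulate the death hazard among patients still under observation.

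**The case against.** The strongest case is that little depends on this. The trial is single-arm, with no PFS or OS hypothesis, comparator or threshold. Section 6.1.2 calls both analyses exploratory. PFS is one unweighted factor in a zone reached with probability of 10% to 13%. The formal list in 2.4 names TTP, and TTP as worded already counts the deaths that PFS drops, so the information would be reported. All of this stands and limits the severity. It does not reconcile the two PFS sentences, and 6.1.2 names PFS, not TTP, for the inconclusive case.

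It is also fair that the two illustrations do not share an assumption. The OS worst case has no deaths before progression, and under that assumption the PFS distortion would be exactly zero. Each must be read alone.

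Complete absence of contact after 6 months is the extreme reading. Section 5.7 plans some survival calls with no end date, 5.8.3 says OS will be determined by visit or telephone, and 10.7 asks for every effort to document outcome. Follow-up beyond the plan's own limits is a resource choice for the sponsor. Moving the PFS time origin is not needed: treatment should start within 72 hours of registration (7.1), so the difference is about 3 days.

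Three stronger readings are tempting, and the documents do not support them:
- That PFS ignores deaths in general. Deaths on study still count; only those after withdrawal, without progression and before alternative therapy are censored.
- That PFS will be overstated by a known amount. No rate of such deaths is given.
- That OS cannot be estimated, or will be overstated by 10 to 18 points. That is the no-contact worst case, and with half of progressed patients followed fully the excess is 1 to 6 points.

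**Conclusion.** The PFS definition is wrong as written and should be corrected; the impact is limited. The contradiction within 6.3 and the direction of its effect need no assumption: PFS is unchanged or raised. The size does. Medians of about 8.1, 8.5 or 9.5 months in place of 7.7 rest on 1, 2 or 4 affected deaths among about 20 events, and those counts are assumed. The primary ORR rule, its error rates and the sample size are unaffected.

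The OS point is secondary. The follow-up sections conflict, and none schedules survival status beyond 6 months for all patients who progress. The figures of 60% to 68% against 50% show what this could mean at worst; they are not a forecast.

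**What to change.** **PFS and TTP**
- In the PFS censoring sentence of 6.3, delete the words for dying and for the date of death. Every death without prior progression and before alternative therapy is then an event, including after withdrawal. Keep the censoring at alternative therapy.
- Analyse PFS in all eligible treated patients, the set 6.1.2 uses for the response proportion, in place of the undefined per protocol population.
- Define TTP with progression as the only event and deaths without progression censored, or drop it.
- Name the same endpoint in 2.1, 2.4 and the synopsis.

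**Survival follow-up**
- Reconcile 4.4 (including study completion), 5.7, 5.8.3 and footnote p of 5.8.6 into one rule that collects survival status after progression for all patients, at least for the 6 months that 5.8.3 already states. Report OS with that follow-up limit. Longer follow-up is the sponsor's choice.

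**Cost.** The PFS and TTP changes are wording. Deaths without progression within the planned follow-up are already to be recorded under 4.4 and 5.8.3; how far that reaches depends on the reconciled rule. Recoding these deaths leaves reported PFS the same or slightly lower, and the change of population could move it slightly either way. The survival rule is one paragraph, plus a few telephone or record checks for patients who progress.

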Appendix B: IMWG Response Criteria

Serum and urine M-protein estimates will be performed every 4 weeks; except for assessment of CR, patients with measurable disease restricted to the SPEP (or UPEP) will need to be followed only by SPEP (or UPEP). Responses will be assessed according to the criteria of the International Myeloma Working Group⁶¹, and characterized as follows:

Response Category	Response Criteria ^a
SCR	CR as defined below plus 
 • Normal FLC ration and • Absence of clonal cells in bone marrow^b by immunohistochemistry or immunofluorescence^c
CR	Negative immunofixation on the serum and urine and disappearance of any soft tissue plasmacytomas and $\leq 5\%$ plasma cells in bone marrow ^b
VGPR	Serum and urine M-protein detectable by immunofixation but not on electrophoresis or 90% or greater reduction in serum M-protein plus urine M-protein level < 100 mg per 24 hours
PR	$\geq 50\%$ reduction of serum M-Protein and reduction in 24 hour urinary M-protein by $\geq 90\%$ or to < 200 mg per 24 hours If the serum and urine M-protein are unmeasurable ^d a $\geq 50\%$ decrease in the difference between involved and uninvolved FLC levels is required in place of the M-protein criteria If serum and urine M-protein are unmeasurable, and the serum free light assay is also unmeasurable, $\geq 50\%$ reduction in plasma cells is required in place of M-protein provided baseline bone marrow plasma cell percentage was $\geq 30\%$ In addition to the above, if present at baseline a $\geq 50\%$ reduction in the size of soft tissue plasmacytomas is also required
SD^e	Not meeting criteria for CR, VGPR, PR, or progressive disease
Relapse Category^f	Relapse Criteria
Progressive disease	Requires only one of the following: Increase of $\geq 25\%$ from baseline in: 
 • Serum M-component and/or (the absolute increase must be ≥ 0.5 g/dl)^g • Urine M-component and/or (the absolute increase must be ≥ 200 mg/24 hours) • In patients without measurable serum and urine M-protein levels the difference between involved and

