	
uninvolved FLC levels, the absolute increase must be $> 10 \text{ mg/dl}$.
 
 • Bone marrow plasma cell percentage, the absolute % must be $\ge 10\%$^h. • Definite development of new bone lesions or soft tissue plasmacytomas increase in the size of existing bone lesions or soft tissue plasmacytomas. • Development of hypercalcemia (corrected serum calcium $> 11.5 \text{ mg/dl}$ or 2.65 mmol/l) that can be attributed solely to the plasma cell proliferative disorder.
Clinical relapse (Not used for TTP or PFS)	Clinical relapse requires one or more of: 
 • Development of new soft tissue plasmacytoma or bone lesions • Definite increase in the size of existing plasmacytomas or bone lesions. A definite increase is defined as a 50% (and at least 1 cm) increase as measured serially by the sum of the products of the cross-diameters of the measurable lesion • Hypercalcemia ($> 11.5 \text{ mg/dl}$ [2.65 mmol/l]) • Decrease in hemoglobin of $\ge 2 \text{ g/dl}$ (1.25 mmol/l) • Rise in serum creatinine by 2 mg/dl or more ($177 \mu\text{mol/l}$ or more)
Relapse from CR ⁱ	Any one or more of the following: 
 • Reappearance of serum or urine M-protein by immunofixation or electrophoresis • Development of $\ge 5\%$ plasma cells in the bone marrow^j • Appearance of any other sign or progression

a. All response categories require two consecutive assessments made at anytime before the institution of any new therapy; all categories also require no known evidence of progressive or new bone lesions if radiographic studies were performed. Radiographic studies are not required to satisfy these response criteria.

b. Confirmation with repeat biopsy not necessary.

c. Presence/absence of clonal cells is based upon the κ/λ ratio by immunohistochemistry and/or immunofluorescence requires a minimum of 100 plasma cells for analysis. An abnormal ration reflecting presence of an abnormal clone is κ/λ of $> 4:1$ or $< 1:2$.

d. Applicable only to patients who have 'measurable' disease defined by at least one of the following three measurements: Serum M-protein $\ge 1 \text{ g/dl}$, Urine M-protein $\ge 200 \text{ mg/24hour}$, Serum FLC assay involved FLC level $\ge 10 \text{ mg/dl}$ provided serum FLC ration is abnormal.

e. Not recommended for use as an indicator of response; stability of disease is best described by providing the time to progression estimates).

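### Section 6.3 times responders first recorded as stable disease to that date rather than to response, and leaves Duration of Overall Response uncomputable for patients whose best response is stable disease

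*Combined protocol and SAP*

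**What the plan says.** Section 6.3 of the combined protocol and SAP gives two adjacent definitions.

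- **Time to Response** runs from first dose "until measurement criteria are first met for [VG]PR or CR or SD (whichever status is recorded first". The next sentence sets the population: "Time to response is computed only for subjects whose best response is [VG]PR or CR".
- **Duration of Overall Response** has a wider population: "The duration of overall response will be computed for subjects whose best response is either [VG]PR or CR or SD". Its start date is narrower: "It will be measured from the time measurement criteria are first met for complete response or partial response".

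Appendix B defines SD as a residual category: "Not meeting criteria for CR, VGPR, PR, or progressive disease". Note e to that table says of SD: "Not recommended for use as an indicator of response", and points to time-to-progression estimates instead. Section 6.1.2 counts partial and complete responses in the response proportion. Nothing elsewhere in the document corrects either definition in 6.3.

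**The concern.** In each definition the population and the event date do not match, and the mismatch runs in opposite directions. Time to Response excludes patients who only ever reach SD, but lets SD stop the clock for those who go on to respond. Duration of Overall Response includes patients who only ever reach SD, but does not let SD start the clock.

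The first fault gives a wrong number. A responder recorded as SD before reaching PR gets a time to response that is really a time to SD. The design expects this path: sections 4.3 and 5.3 allow dexamethasone to be added for SD after 3 cycles, and section 6.1.2 plans to count how many such patients then respond. Under the written rule, those patients' response times would be dated before the drug that preceded the response.

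The second fault gives no number. An analyst who wants a value for SD patients has to make up a start date, and the summary would then mix non-responders with responders.

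**Working it through.** The plan states no figure on this point, so there is none to reproduce. The check applies the two definitions literally to assumed patient histories.

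**Inputs from the documents:** the stopping event, start event and populations in 6.3; SD as the residual category in Appendix B; response assessment at the end of every 28-day cycle (synopsis, study design). **Assumptions:** the histories themselves; status recorded at days 28, 56, 84 and so on; each status dated to its first recording, with confirmation ignored. The bracketed term for partial response in 6.3 is read as PR or VGPR.

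**Formulas**
- Time to Response as written = day of the first SD, PR, VGPR or CR, for patients who ever reach PR or better.
- Time to Response corrected = day of the first PR or better, same patients.
- Duration as written = day of progression minus day of first PR or CR.

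| History by cycle | Time to Response as written | Corrected | Too early by | Duration as written |
|---|---|---|---|---|
| A: SD, SD, PR, PR, PR, PD | 28 | 84 | 56 | 168 − 84 = 84 |
| B: PR ×4, PD | 28 | 28 | 0 | 140 − 28 = 112 |
| C: SD ×5, PD | not in set | not in set | n/a | no start date |
| D: SD, PR, VGPR ×5, PD | 28 | 56 | 28 | 224 − 56 = 168 |

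**Do the two intervals join?** For a responder who progresses, Time to Response plus Duration should equal the time from first dose to progression. For patient A the written rules give 28 + 84 = 112 days, against progression at day 168. The missing 168 − 112 = 56 days are the SD period before response. With the corrected stopping event, 84 + 84 = 168.

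**Dexamethasone conversion.** Take SD at cycles 1 to 3, dexamethasone added, and PR at cycle 4. Time to Response as written is day 28; the first PR is at 4 × 28 = day 112. The recorded response comes before the end of cycle 3 (3 × 28 = day 84), the point after which section 5.3 lets dexamethasone be added.

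**SD-only patient.** C is in the Duration set but has no CR or PR date. Starting the clock at first SD instead would give 168 − 28 = 140 days, longer than the 84 and 112 days of responders A and B. That start date is not in the plan.

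**Sensitivity to the confirmation rule.** Appendix B note a asks for two consecutive assessments for every response category. If SD must meet this too, and is dated to the first of the pair, patient D has only one SD assessment and is timed correctly at day 56. Patient A still has two and stays at day 28.

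**Sensitivity to the schedule.** Section 4.1 places response assessment at the end of cycle 4 or sooner, and section 4.4 after 4, 8 and 12 cycles. If only those three assessments count, SD at cycle 4 followed by PR at cycle 8 is recorded at 4 × 28 = day 112 instead of 8 × 28 = day 224. The fault is the same, with a different size.

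**The case against.** The strongest reply is that little depends on these two quantities. Neither is among the primary or secondary endpoints in sections 2.1, 2.3 and 2.4. Neither enters the 29-patient rule in section 6.1.2; even its inconclusive zone looks to progression-free survival, toxicity and correlative outcomes. No table or decision is tied to either one. All of this stands, and it limits the weight of the point. It does not make the definitions usable as written.

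Three stronger readings are tempting, and the documents do not support them.

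- *A reader might infer that every responder is timed to the first assessment, so that Time to Response tells nothing.* Patients in PR at the first assessment are timed correctly. If the two-assessment rule applies to SD, so are patients with a single SD reading before PR. The schedule is also stated in conflicting ways.
- *A reader might infer that Duration of Overall Response is wrong throughout.* It is not: the values of 84, 112 and 168 days for the three responders above do not change under the correction. The rule fails only for SD-only patients, and there it gives no value rather than a biased one. Mixing non-responders into the summary would take a start date that the plan does not provide.
- *A reader might take the wording as a deliberate disease-control outcome.* In that case SD would both end the first interval and start the second, and SD-only patients would be in both sets. Neither is so.

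It is also fair to say that the Response Rate definition in 6.3 counts SD as well, so one edit could cover all three. But correcting Response Rate alone would leave these two event rules as they are.

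**Conclusion.** The point holds within limits. Time to Response is too early for any responder first recorded as SD, including those who convert after dexamethasone. Duration of Overall Response is correct for responders and cannot be computed for patients whose best response is SD.

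The total error cannot be stated. It depends on how many responders pass through SD, on which assessment schedule applies, and on whether SD needs two consecutive assessments; the documents give no rate for the first and do not settle the other two. For single patients, the assumed per-cycle histories in the table give errors of 0, 28 and 56 days. The consequence is confined to two descriptive outcomes and does not touch the go/no-go rule.

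**What to change.** In section 6.3:

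1. Remove SD from the stopping event for Time to Response.
2. Remove SD from the population for Duration of Overall Response.
3. Use one event, the first date on which criteria for PR or better (PR, VGPR, CR or sCR) are met, both to end Time to Response and to start Duration. Naming the categories also clears up the bracketed partial-response term.
4. Describe SD patients through the time-to-progression estimates, as Appendix B note e advises. Time to progression is already a secondary endpoint; note that 6.3 defines it to end at progression or death.
5. Make the edit together with the separate correction of SD in the Response Rate definition.

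The cost is two deletions and one aligned event definition, made before analysis. No new data are needed, and sample size and treatment do not change.
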